10.6.7.1 Reporting of Infusion Reactions

The signs and symptoms of an infusion reaction usually develop during or shortly after drug infusion and generally resolve completely within 24 hours of completion of the infusion.

Infusion reactions should be recorded so that the presenting sign/symptom is part of the reported AE term(s) (e.g., chills or infusion reaction, fever). Acute infusion reactions should not be classified as anaphylaxis unless symptomatic bronchospasm and/or allergy-related edema/angioedema is/are the principal clinical manifestation(s). Refer to Appendix 5 for the clinical criteria for diagnosis of anaphylaxis.

The start of the infusion reaction with respect to the administration of the investigational product as well as the duration of each symptom should be recorded.

The intensity of the infusion reaction (refer to Section 10.6.5.4 for definitions of mild, moderate, or severe infusion reactions) and causal relationship (i.e., related or not related) to the investigational product (refer to Section 10.6.5.3) should be determined and reported.

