
Screening Period (Day –28 to Day –1): At the Screening visit, the Investigator will review the written informed consent form (ICF) with each subject to ensure that the subject understands the study and the study procedures. The subject will read, sign, and date the ICF and other locally applicable documents. Screening evaluations used to determine the subject’s study eligibility must be completed within the Screening Period (Day –28 to Day –1) prior to starting treatment on Day 1 (Week 0), and include a baseline sigmoidoscopy with biopsy being completed within 7 to 28 days prior to Day 1. For subjects who are rescreened, the original screening sigmoidoscopy can be used to satisfy the entry criteria if obtained within 42 days prior to Day 1. All sigmoidoscopy procedures will be performed using a flexible sigmoidoscope.
 
Double-blind Treatment Period (Weeks 0 to 12/52): Each subject must be carefully monitored at the investigative site for signs of acute, potential dose-limiting toxicity infusion reactions during and for at least 3 hours following the completion of the first and second intravenous (IV) infusions of investigational product, and for at least 1 hour following all other IV infusions. In addition, a phone call to each subject will be conducted at approximately 48 to 72 hours following the completion of the first and second infusions for any subject who does not return for a visit at the investigative site.
 
Induction Therapy: Week 0 to Week 12 (Last Dose at Week 10) Double-blind Induction Therapy is separated into Part A for administration of multiple ascending IV doses of KHK4083 (or placebo) to subjects in Cohorts 1 - 3 and Part B for administration of the recommended IV dose (one of three dose levels identified in Part A) of KHK4083 (or placebo) to subjects in Cohort 4. Subjects in each cohort will be randomly assigned in a 3:1 ratio to receive KHK4083 or placebo by IV infusion over 60 minutes (± 10 minutes).
 
Induction Therapy - Part A: In the first 3 cohorts, 27 subjects (9 subjects/cohort) will receive KHK4083 and 9 subjects (3 subjects/cohort) will receive placebo once every 2 weeks (Weeks 0 to 10) as follows: Cohort 1: 1.0 mg/kg or placebo Cohort 2: 3.0 mg/kg or placebo Cohort 3: 10 mg/kg or placebo
 
The cumulative safety data available after the first 8 of 12 subjects randomized in Cohort 1 will be evaluated by the Safety Monitoring Committee at Week 4 (~Day 29) to assess whether dosing will continue for subjects within Cohort 1 and if investigational product will be administered at the next higher dose level for subjects in Cohort 2. For Cohorts 2 and 3, the cumulative safety data available after the first 8 subjects in each cohort at Week 4 (~Day 29) with the first 4 subjects in each cohort at Week 6 (~Day 43) will be evaluated for continuation of all of the subjects and for dose escalation in the next cohort, i.e., Cohort 3 in Part A and Cohort 4 in Part B, respectively. The Safety Monitoring Committee and Sponsor may dose-reduce cohorts or not escalate to the planned doses based upon review of safety data.
		

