Although mild infusion reactions require no intervention and no interruption of the infusion, investigators are permitted to interrupt the infusion for mild reactions, observe the subject for resolution of any signs/symptoms, and restart the infusion at one-half the infusion rate originally prescribed if the reaction substantially resolves. The rate of the remaining infusion may be gradually escalated to the originally prescribed rate based on the subject's subsequent tolerance and Investigator judgment. For subjects who continue treatment, subsequent infusion(s) may be recommended to be administered at a slower infusion rate.

If a moderate infusion reaction occurs, stop the infusion for at least 15 to 30 minutes. Paracetamol orally and diphenhydramine 50 mg IV or an equivalent anti-histamine may be administered. If symptoms abate, re-start the infusion at one-half the previous rate; if symptoms recur, permanently discontinue the infusion. For reactions that do not abate after 30 minutes, worsen or recur, the Investigator should use their medical judgment to consider additional medical measures.

For any subject experiencing an acute infusion reaction of severe intensity, the infusion must be immediately discontinued and the subject must receive immediate medical/nursing assessment and indicated supportive management per the institutional standard of care and local Investigator judgment until the signs/symptoms of the reaction have resolved.

If consistent mild and/or moderate infusion reactions are observed, the Sponsor (i.e., Medical Monitor and/or a representative from Drug Safety Surveillance) and the Investigator (or designee) may recommend the pretreatment of subjects or a slower infusion rate. In the event that any subject experiences an acute infusion reaction considered to be an SAE, there

may be a decision to introduce, for all subjects, a slower infusion rate for administration of the investigational product, and/or a mandatory pre-medication regimen (e.g., anti-emetics; H1 or H2 blockers; and/or corticosteroids), and/or dose-reduction in a cohort.

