8.1 Adverse events

The onset date of an adverse event will be compared to the date of investigational product dosing to determine if the adverse event is treatment-emergent or not. Adverse events with an onset date on or after the first date of investigational product dosing will be classified as treatment emergent adverse events (TEAEs). If the adverse event onset date is missing or partial, the date will be compared as far as possible with the date of investigational product dosing. Adverse events will be assumed to be TEAEs unless there is clear evidence (through comparison of partial dates) to suggest that the adverse event started prior to receiving the dose of investigational product.

TEAE will be summarized in a table that presents the number and percentage of subjects with any TEAE, with any serious TEAE, with any drug-related TEAE, with any TEAE leading to discontinuation and death overall and within each treatment period (Double-Blind Induction Therapy Period, LTE Therapy Period, and OLE Therapy Period) by treatments (each KHK4083 dose level versus placebo). It will also include the total number of adverse events in each of these categories. All TEAEs will be summarized showing the number and percentage of subjects for each event with a start time within the treatment period (i.e., Double-Blind Induction Therapy Period, LTE Therapy Period, and OLE Therapy Period) and by treatments (each KHK4083 dose level versus placebo) during Induction Therapy or KHK4083 dose level versus placebo during OLE /LTE Therapy Period. All TEAEs will be summarized by SOC and Preferred Term as well as by Preferred Term in decreasing frequency. Two additional summary tables are presented for serious TEAEs and Related TEAEs.

	Forms			
	Title	Statistical Analysis Plan Template		
	Code	Version	Effective Date	Page
	FRM_ST03_032	01	23 Apr 2015	35 of 53

Listings of all adverse events (including non-treatment-emergent events) will be provided. This listing will be presented by dose cohort and will include site-subject identifier, adverse event (SOC, Preferred Term, reported term), start date, stop date, study day, severity grade, seriousness, relationship to drug, action taken with study treatment, and outcome. Also SAEs will be listed in a similar format as described above. Deaths which are adverse events leading to death, adverse events leading to discontinuation and adverse events with withdrawal of investigational product also will be listed in the same manner.

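### No planned output counts subjects with an infusion reaction by dose, although the protocol monitors these reactions as potentially dose-limiting and collects dedicated data on them

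*Protocol*

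**What the plan says.** **Monitoring.** The Protocol synopsis has each subject watched on site for "signs of acute, potential dose-limiting toxicity infusion reactions during and for at least 3 hours" after the first two infusions, and for at least 1 hour after the others. Section 8.1.3.3 repeats this. It also allows pretreatment or a slower infusion to be recommended: "If consistent mild and/or moderate infusion reactions are observed".

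**Recording.** Protocol 10.6.7.1 says: "Infusion reactions should be recorded so that the presenting sign/symptom is part of the reported AE term(s". Its examples include a bare symptom (chills) and a term that can keep the words infusion reaction. It also asks for "The start of the infusion reaction with respect to the administration of the investigational product", the duration of each symptom, a related or not-related judgement, and "The intensity of the infusion reaction (refer to Section 10.6.5.4 for definitions of mild, moderate, or severe infusion reactions". The 10.6.5.4 scale turns on whether the infusion is interrupted or stopped. The general scale in 10.6.5.2 turns mainly on interference with daily activities.

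**Coding.** Protocol 10.6.5.1 has the sponsor code events in MedDRA and gives no grouping rule for infusion reactions.

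**Tabulation.** Protocol 12.5 plans tables by PT and SOC. SAP 8.1 says: "All TEAEs will be summarized by SOC and Preferred Term as well as by Preferred Term in decreasing frequency", with further tables for serious and related events. SAP 9.4 also breaks events down by relationship, maximum severity and discontinuation. The Week 12 list in SAP 9.4.1 has four adverse event tables: overall, SOC/PT, related and serious.

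**The concern.** The protocol sets infusion reactions apart at collection, but the SAP does not take them up again at analysis. It contains no definition of the event set, no grouping rule and no table, figure or listing title for them.

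The recording rule makes the gap matter. Because a bare symptom is an acceptable term, SOC/PT tables can scatter one kind of event over several rows. The reader cannot rebuild the rate by adding rows, for two reasons:

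- A subject with two symptoms sits in two rows.
- A row for chills or fever also holds events that had nothing to do with an infusion.

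The primary objective of Part A is safety and tolerability across ascending doses. The proportion of subjects reacting at each dose bears directly on that, and a reader of the study report would look for it. It cannot simply be borrowed from the Phase 1 study, where Protocol 8.1.3.1 says 10 mg/kg was given over 120 minutes; here all doses are infused over about 60 minutes. That is an observation about comparability, not about which rate is right.

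**Working it through.** The plan states no infusion-reaction figure, so there is nothing to reproduce. The check is whether any planned output delivers the rate, followed by an illustration of what could be lost.

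**Step 1: what is collected against what is planned.**

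| Item in Protocol 10.6.7.1 | Use in the SAP |
|---|---|
| Event identified as an infusion reaction | No definition or grouping in 8.1; no title in 9.4, 9.4.1, 9.5 or 9.6 |
| Onset relative to dosing | Not in any table; the listing described in 8.1 has dates and study day, not time from infusion |
| Duration of each symptom | Start and stop dates in the listing only |
| Intensity per 10.6.5.4 | Can enter the maximum-severity tables (14.3.1-3.1 to -3.3) term by term, mixed with grades from 10.6.5.2; no such table in 9.4.1 |
| Related or not related | Relationship tables, term by term |

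The overall summary tables (14.3.1-1.1 to -1.4) count subjects with any, serious, drug-related or discontinuation-leading events, and deaths. None isolates infusion reactions.

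**Step 2: one hypothetical dose group.** Nine active subjects per Part A cohort comes from Protocol 12.3.4. Assume three react, each with a different symptom coded to its own PT.

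- Subject-level rate: 3/9 = 33.3%. The exact (Clopper-Pearson) limits are the 2.5% quantile of Beta(3, 7) = 0.075 and the 97.5% quantile of Beta(4, 6) = 0.701.
- Each PT row: 1/9 = 11.1%. The limits are the 2.5% quantile of Beta(1, 9) = 0.003 and the 97.5% quantile of Beta(2, 8) = 0.482.

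The planned table would show three rows of 11%. It would not show 33% (7.5% to 70.1%).

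**Step 3: how the loss varies with coding.** Assume each subject reacts independently with probability p, and each reactor is coded to one of k equally likely PTs. The table gives the average size of the largest single PT row over 20,000 simulated groups. The 27 subjects are those planned at the recommended dose (Protocol 12.3.4). The values of p and k are assumptions; neither document gives them.

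| n | p | Mean reactors (n × p) | k = 1 | k = 2 | k = 4 |
|---|---|---|---|---|---|
| 9 | 0.33 | 2.97 | 2.96 | 2.14 | 1.68 |
| 27 | 0.20 | 5.40 | 5.41 | 3.62 | 2.59 |

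With one PT nothing is lost, apart from simulation error. With four, the largest row holds about 1.68/2.97 = 57% of reactors in the small group and 2.59/5.40 = 48% in the larger one.

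**The case against.** The other side has several good arguments.

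- **The term need not lose the words.** The symptom is only part of the term, and one example can keep the words infusion reaction. Protocol 10.6.7 also prefers a diagnosis to symptoms when one is known. A reader might infer that every reaction is filed under its symptom; the text does not say that. It leaves the outcome to site wording, so an infusion-reaction row, if one appears, may be an incomplete count.
- **Tabulation and intensity.** A reader might infer that events are tabulated by PT alone and that infusion-reaction intensity goes unanalysed. Both are too strong. SAP 9.4 has several breakdowns, and the 10.6.5.4 grade can naturally feed the maximum-severity tables. What is missing is a view of these reactions as a group.
- **Status of the event.** A reader might infer that infusion reactions are the trial's one defined dose-limiting toxicity. The protocol only asks sites to watch for reactions that might be dose-limiting. Its termination examples (7.5.2) are infections and SUSARs, and 10.1.2 lists no infusion-reaction rate among the safety endpoints. The SAP therefore follows its protocol, and the gap is not a contradiction between the two.
- **Dose decisions.** These rest with the Safety Monitoring Committee, on cumulative data under a separate charter (Protocol 6.3), not on SAP tables.
- **Other routes.** SAP 4.1 promises listings of all eCRF data, SAP 6.1 shows that infusion times are recorded, the shells are a separate document, and SAP section 1 allows unlisted exploratory analyses. With about 60 subjects, case review is feasible.

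The last point reduces the harm but does not remove the gap. A hand count from listings, or an analysis chosen after unblinding, has no event definition fixed in advance.

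**Conclusion.** The point holds as an omission in the planned outputs. The protocol requires dedicated data on infusion reactions, and no listed table, figure or listing turns them into a subject-level count by dose or a group-level display of the 10.6.5.4 intensity.

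The size is unknown. It runs from no loss, if all events share one PT, to a largest row holding about half of the reactors under the four-term assumption. The 33% against 11% contrast is a constructed example and should not be read as an expected bias. No conclusion about past or future dose decisions follows.

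The verdict assumes that the shells and the committee charter, which were not available, contain no such output. Because the Part A primary objective is tolerability and the remedy is cheap, the table should be added.

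**What to change.** Add one table to SAP 9.4 and to the Week 12 list in 9.4.1. It should give the number and percentage of subjects with at least one infusion reaction, each subject counted once, by dose level and placebo, by infusion number and by 10.6.5.4 intensity.

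- **Event set.** Use events the investigator recorded as infusion reactions under Protocol 10.6.7.1, whatever their relationship to product.
- **Fallback.** If the database cannot identify those events, use all treatment-emergent events with onset in a window after the start of infusion, again regardless of relationship. The SAP must fix that window before unblinding. The 24 hours mentioned in Protocol 8.1.3.3 and 10.6.7.1 describes when reactions usually resolve, so it is not a source for an onset window.
- **Labelling.** Keep induction separate from the open-label extension. SAP Table 2, footnote 3, leaves placebo-randomised subjects under the Placebo label there although they receive KHK4083.

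The cost is a small amount of programming, plus a check of whether the eCRF carries an infusion-reaction identifier. The protocol already requires the information the table needs.

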10.6.8 Other Significant Adverse Events

Clinical laboratory abnormalities that qualify as AEs (other than those meeting the definition for serious) and/or any events that lead to an intervention (including premature discontinuation or prolonged infusion time of the investigational product, or significant additional concomitant therapy) will be reported and evaluated as AEs.

Any clinically important changes noted during interim or final physical examinations, ECGs, x-rays, or any other potential safety assessments, whether or not these procedures are required by the protocol, must also be collected, and if serious recorded on the SAE Report form, when possible, in order for the Sponsor to collect additional information about that

abnormality, including information regarding relationship to KHK4083 or placebo, any action taken, and resolution.

10.6.9 Pregnancy Reporting

This process is aimed at ensuring the appropriate monitoring of the potential risk related to investigational product exposure of pregnant women and/or fetuses as well as the risks associated with exposure of a father, regarding congenital abnormalities or birth defects in their offspring. It also ensures compliance with applicable international and local regulations.

The requirements are applicable to all subjects following exposure to the investigational product (KHK4083 or placebo).

Female study subjects: The subject must be advised by the Investigator to inform the Investigator immediately if she suspects she may be pregnant.

Male study subjects: The subject must be advised by the Investigator to inform the Investigator immediately if they suspect their partner became pregnant after the subject was administered investigational product.

When a study subject reports a pregnancy (post-KHK4083 administration) to the Investigator, KHK4083 should be stopped immediately and a pregnancy test should be arranged for the subject (or their partner) by the Investigator within 7 days of the pregnancy being reported.

In the case of pregnancy, the Investigator must immediately notify the Sponsor of this event and report the pregnancy on the Pregnancy Surveillance Form. This includes a study subject as well as the partner of a study subject who becomes pregnant while the subject was receiving investigational product. Every attempt will be made to follow the pregnancy to conclusion to obtain information regarding the outcome.

10.6.10 Safety Management during the Study

The Sponsor has primary responsibility for the ongoing medical review of safety data throughout the study. This includes AEs considered to be medically significant and making recommendations with the input of the Medical Monitor regarding further conduct of the study. The Safety Monitoring Committee will meet as needed in addition to the scheduled times according to the monitoring plan. Refer to Section 6.3 for details on the safety monitoring plan.

10.7 Appropriateness of Measurements

All assessments and measurements are appropriate and generally regarded as standard care or medical practice.

11 DATA HANDLING AND QUALITY ASSURANCE

11.1 Electronic Case Report Forms and Source Documentation

Subject data will be entered into study eCRFs, transmitted electronically to the data management vendor and the Sponsor, and combined with data provided from other sources. Management of clinical data will be performed in accordance with applicable industry standards and data cleaning procedures to ensure the integrity of the data. It is the responsibility of the investigative site to prepare and maintain the adequate and accurate eCRFs that have been designed by the Sponsor to record all observations and other data pertinent to the clinical investigation. The eCRFs are used to record information collected in the performance of this study and that will be entered into the electronic data capture (EDC) system. These eCRFs are organized as an ordered series of electronic data entry modules specific for each scheduled and unscheduled study visit.

The investigative site EDC users will exercise due diligence in ensuring that study data are entered accurately and in their entirety from the investigative site's source documents and flow sheets into the appropriate data entry fields. Only staff listed on the "Delegation of Authority" page in the study file notebook and who have been appropriately trained to use the EDC system will be issued a user identification code allowing them to make entries and edits to the EDC system and to respond to queries. Only the Investigator will be issued a user identification code allowing the application of an electronic signature to a completed study subject record signifying the data has been reviewed and verified as complete and accurate.

By signing this protocol, the Investigator agrees to treat all subject data used and disclosed in connection with this study in accordance with all applicable privacy laws, rules and regulations. In addition for US investigative sites, compliance is required with all applicable provisions of the Health Insurance Portability and Accountability Act (HIPAA) and its implementing regulations.

11.2 Clinical Data Management

Data management will be carried out by the contract research organization selected by the Sponsor. The Sponsor will provide oversight and will have the overall responsibility for the

processing and quality control of the data. The handling of data, including data quality control, will comply with all applicable regulatory guidelines.

Management of clinical data will be performed in accordance with applicable industry standards and data cleaning procedures to ensure the integrity of the data, e.g., removal of errors and inconsistencies in the data.

11.3 Archiving

Electronic case report forms, including queries and audit trails, will be retained by the Sponsor, while the Investigator will receive a copy of the site data in the Portable Document Format on a compact disc-read only memory following study completion.

All study documentation at the investigative site and the Sponsor's site will be archived in accordance with ICH E6-GCP.

